INVESTIGATIONAL PRODUCT	⁶⁸ Ga-PSMA-11; also known as: 
 • DFKZ-11 • HBED-CC PSMA • The “Heidelberg compound”
PRIMARY OBJECTIVE	To evaluate ⁶⁸ Ga-PSMA-11 PET/CT for detection of recurrent prostate cancer after initial therapy in patients with elevated PSA
SAMPLE SIZE	200 participants
GOALS	
Prospective single-center, single-arm study.
 
HYPOTHESES
 
 1. At least 30% of these patients will have one or more lesions detected on ⁶⁸Ga-PSMA-11 PET/CT. 2. ⁶⁸Ga-PSMA-11 PET/CT will have sensitivity and specificity of at least 70% in this context. 
STATISTICAL TEST
 
We will calculate point estimates and 95% confidence intervals for:
 
 1. Percentage of patients who had true lesions. 2. Sensitivity and specificity of ⁶⁸Ga-PSMA-11 PET/CT. 
STATISTICAL POWER AND SAMPLE SIZE
 
We expect to recruit 200 patients over the course of this trial. The number of lesions cannot be predicted at this time, however, if our expectation of a 30% discovery rate is correct, the resulting confidence interval would be roughly +/- 7 percentage points, and confidence intervals for specificity/sensitivity would be roughly +/- 10 percentage points.

SCHEMA

Eligible participant with prostate cancer

LIST OF ABBREVIATIONS AND DEFINITION OF TERMS

Ga-68; ^{68}Ga	Gallium-68
IRB	Institutional Review Board
IV	Intravenous
MRI	Magnetic resonance imaging
NPV	Negative predictive value
PPV	Positive predictive value
PET	Positron emission tomography
SUV	Standardized Uptake Value
PSMA	Prostate Specific Membrane Antigen

1. OBJECTIVE

Specific Aim

To evaluate ^{68}Ga -PSMA-11 PET/CT for detection of recurrent prostate cancer after initial therapy in patients with elevated SA.

2. BACKGROUND

2.1 Preliminary information

Data from the American Cancer Society suggests that for 2015 in the United States prostate cancer will continue to be the leading non-cutaneous cancer diagnosis in males with 220,800 estimated new cases, and has the second highest mortality (after lung) with 27,540 estimated deaths (1). Subsequent treatment is multifaceted and may involve observation, surgery (prostatectomy), radiation therapy (external beam or brachytherapy), hormonal therapy, chemotherapy, or a combination of these (2-4).

Up to 40% of the patients with prostate cancer develop biochemical recurrence within 10 years after initial treatment (5). Usually an increase of the PSA-level precedes a clinically detectable recurrence by months to years (6). However, it cannot differentiate between local, regional or systemic disease with the necessary precision that is essential for further disease management (7).

Morphological imaging methods exhibit considerable limitations: sensitivity ranges between 25% and 54% for the detection of local recurrence by transrectal ultrasound (TRUS) or contrast-enhanced CT and is moderately improved by using functional MRI techniques (7-9). The sensitivity for detection of lymph node metastases of CT or MRI is reported to be 30-80% (10). Ultra-small particles of iron oxides (USPIOs) proved to be very effective, but are yet to be approved by regulatory authorities (11). Bone metastases presenting as osteoblastic lesions can be effectively detected by bone scintigraphy, PET, CT and MRI (12, 13).

Various targets have been addressed by molecular imaging to improve the detection of recurrent prostate cancer. PET tracers such as ^{18}F - or ^{11}C -labeled choline and ^{11}C -acetate have been investigated for the diagnosis of recurrent (14-16) prostate cancer. Their feasibility in primary diagnosis is limited because of uptake in benign tissue such as benign prostatic hyperplasia or inflammatory lymph nodes (9, 17). In addition, fluorinated versions are not available in the United States, while ^{11}C -labeled tracers cannot be widely used due to the requirement for an on-site cyclotron due to the short half-life. ^{18}F -FACBC, a new synthetic amino acid, might be superior when compared to ^{11}C -choline PET/CT (18).

However, recent work indicates that ^{18}F -FACBC uptake in prostate cancer is similar to that in BPH nodules (19). Prostate-specific membrane antigen (PSMA) continues to elicit high interest. This cell surface protein is significantly overexpressed in prostate cancer cells when compared to other PSMA-expressing tissues such as kidney, proximal small intestine or salivary glands. It therefore provides a promising target for prostate cancer-specific imaging. Recently methods have been developed to label PSMA ligands with ^{68}Ga and ^{18}F . Initial experience suggests that these novel tracers can detect prostate cancer relapses and

metastases with high contrast by binding to the extracellular domain of PSMA, followed by internalization (20, 21). However, these promising agents do not detect all recurrences.

Although choline-based PET/CT is widely used outside the US for imaging prostate cancer, there have been numerous studies reporting a low sensitivity and specificity, especially at low prostate specific antigen (PSA) levels (22, 23). Consequently, improved imaging of prostate cancer is necessary. One novel promising method is PET imaging with ¹⁸F-FACBC, a new synthetic amino acid. Recent evaluations by Nanni et al. indicate that this tracer might be superior when compared to choline PET/CT (24). However, recent work indicates that ¹⁸F-FACBC uptake in prostate cancer is similar to that in BPH nodules (25).

In addition, prostate-specific membrane antigen (PSMA) recently has received increased attention (26). This cell surface protein is significantly overexpressed in prostate cancer cells when compared to other PSMA-expressing tissues such as kidney, proximal small intestine or salivary glands (27). It therefore provides a promising target for prostate cancer-specific imaging (28). Recently methods have been developed to label PSMA ligands with ⁶⁸Ga enabling their use for PET imaging and therapy (29). Initial experience with PET/CT using Glu-NH-CO-NH-Lys-(Ahx)-[⁶⁸Ga(HBED-CC)] (⁶⁸Ga-PSMA-11) as a ⁶⁸Ga-labelled PSMA ligand suggests that this novel tracer can detect prostate cancer relapses and metastases with high contrast by binding to the extracellular domain of PSMA, followed by internalization (30). Improved detection of occult metastatic disease will improve treatment efficacy by enabling better patient selection for treatment and prompting more extended pelvic node treatment with surgery or radiation for patients with evidence of nodal metastases outside the normal lymph node treatment area.

We conducted a pilot phase evaluation of ⁶⁸Ga-PSMA-11 under an RDRC-approved protocol at Stanford University. Ten men (age range: 67 to 83 year-old; mean \pm SD: 73.1 \pm 5.7) with biochemical recurrence of prostate cancer (PSA range: 2.6-36.4; mean \pm SD: 12.4 \pm 10.6) were enrolled. PET/CT images were acquired at 51 to 68 minutes (mean \pm SD: 57.4 \pm 6.3) after injection of 3.7 to 4.0 mCi (mean \pm SD: 3.8 \pm 0.1) of ⁶⁸Ga-PSMA. The uptake of ⁶⁸Ga-PSMA-11 was identified as described in previously published studies referenced above.

All participants had multiple standard of care imaging studies (CT, MRI, ¹⁸F-FDG PET/CT, ¹⁸F-NaF PET/CT, ^{99m}Tc MDP bone scan) prior to enrollment that were non-contributory, despite rising PSA values. The participants did not receive treatment in this interval as they were managed under a wait and watch strategy due to no identifiable disease. The interval from biochemical recurrence to the ⁶⁸Ga-PSMA-11 PET/CT scan ranged 5 to 75 months (mean \pm SD: 30.8 \pm 20.4).

Biodistribution and localization of ⁶⁸Ga-PSMA-11

All participants tolerated the procedure without immediate or delayed (up to 7 days) complaints or complications. The areas with the highest ⁶⁸Ga-PSMA-11 accumulation are the lacrimal gland (mean SUV_{max}: 9.3 \pm 3.3 [range: 4.6 to 14.9] and SUV_{mean}: 5.2 \pm 2.3 [range: 2.5 to 8.8]), the parotid gland (mean SUV_{max}: 14.2 \pm 2.6 [range: 9.9 to 19.1] and SUV_{mean}: 11.8 \pm 2.6 [range: 7.2 to 16.1]), the submandibular gland (mean SUV_{max}:

16.8 ± 3.3 [range: 12.3 to 22.7] and SUV_{mean} : 13.5 ± 2.9 [range: 9.8 to 18.1]), small intestine (mean SUV_{max} : 14.6 ± 4.6 [range: 8.2 to 23.4] and SUV_{mean} : 11.0 ± 3.9 [range: 5.6 to 18.5]), kidney (mean SUV_{max} : 35.1 ± 9.9 [range: 14.4 to 46.2] and SUV_{mean} : 25.8 ± 7.5 [range: 12.0 to 36.0]) and bladder (mean SUV_{max} : 35.0 ± 24.7 [range: 9.6 to 78.5] and SUV_{mean} : 26.5 ± 17.4 [range: 7.8 to 67.9]), while moderate uptake was noted in the sublingual gland (mean SUV_{max} : 5.0 ± 2.4 [range: 1.9 to 10.6] and SUV_{mean} : 3.3 ± 1.6 [range: 1.5 to 7.1]), liver (mean SUV_{max} : 6.0 ± 1.3 [range: 4.1 to 9.0] and SUV_{mean} : 4.1 ± 0.8 [range: 3.2 to 5.7]) and spleen (mean SUV_{max} : 8.0 ± 3.3 [range: 2.6 to 12.3] and SUV_{mean} : 6.4 ± 2.7 [range: 2.0 to 10.5]). Other tissues analyzed had low ^{68}Ga -PSMA-11 uptake, with SUV_{mean} of less than 1.7. There were no differences between the ^{68}Ga -PSMA-11 biodistribution at 45 minutes post-injection among the 10 participants (Figure 2). The pattern of ^{68}Ga -PSMA-11 uptake is similar to previous reports.

^{68}Ga -PSMA-11 uptake outside the expected physiologic biodistribution

There were 45 areas of high ^{68}Ga -PSMA-11 uptake that corresponded on the CT images to bone marrow ($n = 13$), retroperitoneal lymph nodes ($n = 12$), mediastinal lymph nodes ($n = 8$), pelvic lymph nodes ($n = 9$), seminal vesicle ($n = 2$), subclavian lymph node ($n = 1$).

[figure not shown]

Figure 1: Maximum intensity projection (MIP) images from 10 participants in the pilot study conducted at Stanford University.

2.2 Study Agent

We will use ^{68}Ga -PSMA-11 as the PET radiopharmaceutical. This agent has previously been identified as DFKZ-11; HBED-CC PSMA; or the “Heidelberg compound.” This is not an FDA-approved product. This protocol is submitted to IND 128379.

2.3 Clinicaltrials.gov

Since ^{68}Ga -PSMA-11 is not an FDA-approved product, we will register the study on clinicaltrials.gov once all approvals will be in place.

2.4 Rationale

In this study, we propose to use a well-established PET isotope, Gallium-68 (^{68}Ga), bound to a PSMA ligand, (ie, ^{68}Ga -PSMA-11), which has high affinity for prostate specific membrane antigen. ^{68}Ga -PSMA-11 has been shown to be superior to other PET tracers used in prostate cancer such as ^{18}F -Fluoroethylcholine (FECH) and ^{18}F -Fluoromethylcholine (31, 32). Therefore, we propose the following aim: to evaluate ^{68}Ga -PSMA-11 PET/CT for detection of recurrent prostate cancer after initial therapy in patients with elevated PSA.

A prior first-in-human study investigated the biodistribution of ^{68}Ga -PSMA-11 and its ability to detect lesions. Thirty-seven men with prostate cancer underwent whole-body PET/CT after an intravenous injection of ^{68}Ga -PSMA-11 (median 121.0 MBq, range 52–212 MBq). Within healthy organs, kidneys and salivary glands demonstrated the highest radiotracer uptake. Lesions suspicious for PC presented with excellent contrast as early as 1 hour post-injection with high detection rates even at low PSA levels (30). In another study, a total of 78 lesions characteristic for prostate cancer were detected in 32 patients using ^{68}Ga -PSMA-11 PET/CT and 56 lesions were detected in 26 patients using choline PET/CT (32). The higher detection rate in ^{68}Ga -PSMA-11 PET/CT was statistically significant ($P = 0.04$). All lesions detected by ^{18}F -fluoromethylcholine PET/CT were also seen by ^{68}Ga -PSMA-11 PET/CT. In conclusion, ^{68}Ga -PSMA-11 PET/CT can detect prostate cancer lesions with improved contrast when compared to ^{18}F -fluoromethylcholine PET/CT, especially at low PSA levels.

[figure not shown]

Figure 2: Red arrows point to a nodular pelvic wall metastasis (a, b, histologically-confirmed) and to small lymph nodes (c, d) which present with clearly pathological tracer uptake in ^{68}Ga -PSMA-11 PET/CT (b and d) only. Yellow arrows point to both catheterized ureters (c, d). Patient presented with a minimal PSA value (0.01 ng/mL) despite visible tumor lesions. The PSMA-11 ligand is therefore able to detect poorly differentiated PC. a + c Fusion of ^{18}F -fluoromethylcholine PET and CT; b + d fusion of ^{68}Ga -PSMA-11 PET and CT.

2.5 Study Design

This is a phase 2-3 study with a total of 200 participants with biochemically recurrent prostate cancer. Eligible participants will undergo baseline assessments at enrollment. Study participants will receive ⁶⁸Ga-PSMA-11 and undergo a PET/CT. All patients will first be seen by a Stanford Cancer Institute physician and then referred if appropriate on clinical grounds to Dr [name] or his colleagues for this study. The following steps will take place.

1. After signed the informed consent document, participants will be given a copy of the signed form.
2. Participant will be asked to drink 1 to 2 glasses of water before arrival at the clinic
3. Participants will be weighed and vital signs (heart rate, blood pressure, respiratory rate, pulse oxymetry) will be recorded
4. Study personnel (eg, technologist) will verify subject identify; radiopharmaceutical identity; dose; and administration route. Participant will be injected IV with 3 to 7 mCi of ⁶⁸Ga-PSMA-11
5. A dose of 20 mg of furosemide is recommended to be injected together with, shortly before, or after administration of the radiotracer in order to minimize PET scatter artifacts from excreted radiotracer accumulation in the kidney and urinary bladder that can occur with ⁶⁸Ga-PSMA-11. However, this is not needed if the scanner can reduce such artifacts during image reconstruction
6. Participant will void immediately prior to the scan
7. Approximately 50 to 100 minutes later, a low-dose CT will be obtained from vertex to mid-thighs; this will use 120 kV and dose modulation based on body habitus, ranging 10 to 105 mA. This will be followed by a static PET emission scan over the same area.
8. If participant agrees, immediately after first scan and without reinjecting ⁶⁸Ga-PSMA-11, a second PET/CT will be acquired to compare standard vs digital PET/CT. The CT will be done for attenuation correction only.
9. Vital signs (heart rate, blood pressure, respiratory rate, pulse oxymetry) will be recorded again at the completion of the study.
10. Participants be dismissed.
11. Participants will be contacted at 24 to 72 hours following the scan in order to capture potential late occurring Adverse Events.
12. Clinical follow-up of participant at 3 to 12 months following the scan in order to analyze secondary endpoints.

The ⁶⁸Ga-PSMA-11 PET/CT may be repeated at the completion of treatment to evaluate response to therapy, if requested by the treating physician.

3. PARTICIPANT SELECTION AND ENROLLMENT PROCEDURES

3.1 Inclusion Criteria

[figure not shown]
- ≥ 18 years-old
- Histopathological-proven prostate adenocarcinoma
- Rising PSA after definitive therapy with prostatectomy or radiation therapy (external beam or brachytherapy)
 - a. Post radical prostatectomy (RP) – AUA recommendation (34)
 - i. PSA greater than 0.2 ng/mL measured after at least 6 weeks from radical prostatectomy
 - ii. Confirmatory persistent PSA greater than 0.2 ng/mL (total of two PSA measurements greater than 0.2 ng/mL)
 - b. Post-radiation therapy –ASTRO-Phoenix consensus definition (35)
 - i. A rise of PSA measurement of 2 or more ng/mL over the nadir
- Able to provide written consent
- Karnofsky performance status of ≥ 50 (or ECOG/WHO equivalent)

3.2 Exclusion Criteria

- Investigational therapy for prostate cancer.
- Unable to lie flat, still or tolerate the study scan.
- Prior history of any other malignancy within the last 2 years, other than skin basal cell or cutaneous superficial squamous cell carcinoma that has not metastasized and superficial bladder cancer.

Study diagram or flow chart**

PCa BCR Study Inclusion Criteria:
As detailed on previous page

3.3 Informed Consent Process

All participants will be provided a consent form describing the study with sufficient information for participants to make an informed decision regarding their participation. Participants must sign the IRB approved informed consent prior to participation in any study

specific procedure. The participant must receive a copy of the signed and dated consent document. The original signed copy of the consent document must be retained in the medical record or research file.

3.4 Study Timeline

3.4.1 Primary Completion:

The study will reach primary completion 36 months from the time the study opens to accrual.

3.4.2. Study Completion:

The study will reach study completion 48 months from the time the study opens to accrual.

4. IMAGING AGENT INFORMATION

4.1 Study Agent

The administered dosage is 111 to 259 MBq (3 to 7 mCi) IV. We will use ^{68}Ga PSMA-11 as the PET radiopharmaceutical. There are 2 publications on dosimetry for ^{68}Ga -PSMA-11 (PMID: 27260521; 28012435). The first lists 0.0236 mSv/MBq for the mean effective dose, while the other indicates 0.0258 mSv/MBq. We used the maximum potential administered activity of 7 mCi and the higher of the reported dosimetry values. Therefore, $259 \text{ MBq} \times 0.0258 \text{ mSv / MBq} = 6.68 \text{ mSv}$.

To summarize the results of the published human studies, there were no observed adverse events to the radiopharmaceutical. The measured dosimetry showed that the critical organ with ^{68}Ga -PSMA-11 is the spleen, followed by the stomach wall, pancreas and bladder wall. The effective dose of ^{68}Ga -PSMA-11 reported (0.0258 mSv/MBq) is similar to those of ^{68}Ga -DOTA-TOC (0.023 mSv/MBq); ^{68}Ga -DOTA-NOC (0.025 mSv/MBq); ^{68}Ga -DOTA-TATE (0.021 mSv/MBq); and ^{68}Ga -NOTA-RGD (0.022 mSv/MBq) (36-39).

4.2 Source of the Study Agent

Molecular Imaging Program at Stanford
Satellite Radiochemistry Facility
[name]
[name]

4.3 Ordering

Ordered in Radiology Information System (RIS), address per above.

4.4 Agent Accountability

RIS is password protected and part of the electronic medical records.

5. IMAGING SPECIFICS

5.1 Modality or Modalities to be used

PET/CT

5.2 Details of Imaging (ie, dynamic, static, number of scans, etc)

Whole-body (skull base to mid-thighs) PET/CT images will be obtained using the GE PET/CT 600 or 690 scanners. In brief, PET/CT images will be acquired in 3D mode at 50 to 100 minutes after injection of 3 to 7 mCi of ^{68}Ga -PSMA-11.

The PET emission scan is corrected using segmented attenuation data of the CT scan. PET images are reconstructed using ordered subset expectation maximization (OSEM) with 2 iterations and 32 subsets for the Discovery 600 scanner and with 2 iterations and 24 subsets for the Discovery 690 scanner. These are the vendor-recommended reconstruction parameters. Images will be reviewed and analyzed using Advantage Workstation version 4.6 (GE Healthcare).

5.3 Details of processing/analysis

The lesions will be analyzed by Nuclear Medicine physicians blinded to the diagnosis and results of the other scan, in a randomized order to avoid bias. ^{68}Ga -PSMA-11 PET data will be interpreted by 3 different readers in a random order at separate reading sessions. Cross sectional imaging from the PET will be available for anatomic correlate.

6. STUDY PROCEDURES

6.1 Criteria for Removal from Study

The Protocol Director may withdraw subjects from the study for one or more of the following reasons: failure to follow the instructions of the Protocol Director and/or study staff; determination that continuing the participation could be harmful to the subject; the study is cancelled or other administrative reasons.

6.2 Alternatives

The alternative is to not participate in the study.

7. STUDY CALENDAR

	Pre-Study	Scan Date	24 - 48 Hours Post-Scan	3-12 Months Post-Scan	12 Months (End-of-Study)
Informed consent	X				
Demographics	X				
Medical history	X				
^{68}Ga -PSMA-11		X			
Follow-up Call to Participant			X		
Clinical Follow-up				X	
Data analysis					X

8. ADVERSE EVENTS AND REPORTING PROCEDURES

8.1 Potential Adverse Events

The administration of the radioactive substance will feel like a slight pinprick when given by IV injection. Patients who are claustrophobic may feel some anxiety while positioned in the scanner. Also, some patients find it uncomfortable to hold one position for more than a few minutes. The subjects will not feel anything related to the radioactivity of the substance in their body. Because the radioactivity is very short-lived, the radiation exposure is low. The substance amount is so small that it does not affect the normal processes of the body.

This research study involves exposure to radiation from one ^{68}Ga -PSMA PET/CT. The effective dose from one typical maximum of 259 MBq (range: 3-7 mCi) administration of ^{68}Ga -PSMA is 6.68 mSv. The effective dose from one CT attenuation scan is 3 mSv.

Therefore, the total effective dose from the ^{68}Ga -PSMA PET/CT scan is 9.68 mSv, approximately equal to 19.4% of the limit that radiation workers (for example, a hospital x-ray technician) are allowed to receive in one year.

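### Section 8.1 counts radiation from one PET/CT (9.68 mSv), but Section 2.5 offers an optional same-session second PET/CT whose CT dose is not counted

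*Combined protocol and SAP*

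**What the plan says.** Section 8.1 (Potential Adverse Events) describes the exposure without qualification: "This research study involves exposure to radiation from one" PET/CT. It takes 6.68 mSv for an injection of 259 MBq and adds a single CT: "The effective dose from one CT attenuation scan is 3 mSv". The sum is 9.68 mSv, given as about 19.4% of a radiation worker's annual limit.

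Section 4.1 (Study Agent) explains the tracer component: "We used the maximum potential administered activity of 7 mCi and the higher of the reported dosimetry values". The dose is therefore meant as an upper figure for one injection.

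Section 2.5 (Study Design) sets out the imaging. Step 7 describes the first CT: "this will use 120 kV and dose modulation based on body habitus, ranging 10 to 105 mA". Step 8 then provides that, for participants who agree and with no further injection, "a second PET/CT will be acquired to compare standard vs digital PET/CT. The CT will be done for attenuation correction only". No settings or dose are given for this second CT. The last paragraph of Section 2.5 adds that the study scan "may be repeated at the completion of treatment to evaluate response to therapy, if requested by the treating physician".

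**The concern.** The two sections disagree on how many PET/CT acquisitions the study involves. A participant who accepts the step 8 scan has two CTs, while Section 8.1 counts one. The extra scan is a protocol procedure done to compare scanners, so its exposure belongs where the protocol states its radiation risk. The 9.68 mSv figure is the only total in that section, and it leaves this CT out.

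What is at stake is the accuracy of a stated safety number. No endpoint, estimate or sample size uses it. The consent pages are not in the review copy, so nothing is claimed about what participants are told.

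**Working it through.** **Inputs**

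- Activity: 111 to 259 MBq, or 3 to 7 mCi (Section 4.1), so 259/7 = 37 MBq per mCi.
- Dose coefficient: 0.0258 mSv/MBq, the higher of the two values cited (Section 4.1).
- CT dose: 3 mSv for one attenuation CT (Section 8.1).
- Second CT: no dose given. Assumed to be 3 mSv, with 1.5 mSv as an illustrative lower value.
- Annual worker limit: not stated. 9.68/0.194 = 49.9, so 50 mSv is implied.

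**Reproducing the printed figure**

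- Tracer: 259 × 0.0258 = 6.68 mSv.
- Total: 6.68 + 3 = 9.68 mSv, and 9.68/50 = 19.4%.

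The figure reproduces exactly with one injection and one CT, so it contains no second CT.

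**Same-session total at 7 mCi with the second scan**

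There is no reinjection, so only a CT is added.

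| Second CT | Total (mSv) | Share of 50 mSv | Increase over 9.68 |
|---|---|---|---|
| 3 mSv | 6.68 + 3 + 3 = 12.68 | 25.4% | 3/9.68 = 31% |
| 1.5 mSv | 6.68 + 3 + 1.5 = 11.18 | 22.4% | 1.5/9.68 = 15% |

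**Dependence on activity, two 3 mSv CTs**

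| Activity | Total (mSv) |
|---|---|
| 3 mCi (111 MBq) | 111 × 0.0258 + 6 = 8.86 |
| 5 mCi (185 MBq) | 185 × 0.0258 + 6 = 10.77 |
| 7 mCi (259 MBq) | 259 × 0.0258 + 6 = 12.68 |

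**Activity above which the true total exceeds 9.68 mSv**

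- Second CT 3 mSv: (9.68 − 6)/0.0258 = 142.6 MBq, or 3.86 mCi.
- Second CT 1.5 mSv: (9.68 − 4.5)/0.0258 = 200.8 MBq, or 5.43 mCi.

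**At the pilot activities**

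Section 2.1 reports imaging "after injection of 3.7 to 4.0 mCi", with a mean of 3.8. With two 3 mSv CTs:

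- 3.7 mCi: 136.9 × 0.0258 + 6 = 9.53 mSv.
- 3.8 mCi: 140.6 × 0.0258 + 6 = 9.63 mSv.
- 4.0 mCi: 148 × 0.0258 + 6 = 9.82 mSv.

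**Repeat study after treatment (secondary)**

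With both sessions at 7 mCi and 3 mSv per CT:

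- No second CT in either session: 9.68 + 9.68 = 19.36 mSv.
- Second CT in one session: 12.68 + 9.68 = 22.36 mSv.
- Second CT in both sessions: 12.68 + 12.68 = 25.36 mSv.

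The last case supposes that the optional scan is offered again, which the protocol does not say.

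**The case against.** The strongest reply is that nothing printed is miscalculated. Section 8.1 gives a per-scan dose, does not call it a study maximum, and describes the core procedure, which the study calendar in Section 7 shows as one scan date. The extra scan is opt-in and adds no tracer. That defends the 9.68 mSv figure but not the sentence on what the study involves, because step 8 itself describes a second PET/CT.

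A second reply is that 3 mSv for the extra CT is an assumption. The first CT also serves as an anatomic reference (Section 5.3: "Cross sectional imaging from the PET will be available for anatomic correlate"), while the second is for attenuation correction only, so its dose could be lower. This stands as a limit on the size. Against it, Section 8.1 describes its own 3 mSv scan as an attenuation CT, which makes 3 mSv a reasonable working value until the sponsor supplies the real one.

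Third, the printed figure assumes maximum activity and so has slack at lower activities. That is true up to about 3.86 mCi with a 3 mSv second CT, and the pilot doses lie around that point. Most of the permitted 3 to 7 mCi range lies above it, and at every activity the second CT remains uncounted.

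Finally, the repeat study depends on the treating physician, and the protocol does not say whether it counts as research exposure. It is therefore kept as a side point; the main conclusion does not need it.

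**Conclusion.** The concern holds as a minor inconsistency. Section 8.1 limits the study's radiation to one PET/CT, and Section 2.5 offers a second with its own CT that no section in the review copy counts. That omission is certain from the text.

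Its size is conditional. At maximum activity the same-session total is about 12.68 mSv instead of 9.68 mSv if the second CT delivers 3 mSv, and 11.18 mSv if it delivers 1.5 mSv. The percentages rest on the implied 50 mSv limit. Only participants who accept the second scan are affected, and the excess over the printed figure is near zero at the pilot activities and largest at 7 mCi.

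**What to change.** The sponsor should first confirm the dose of the second CT. Section 8.1 should then replace the one-scan statement with wording such as:

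> Up to 9.68 mSv (19.4% of the annual worker limit) for one PET/CT, and up to about 12.68 mSv (25.4%) in the same session if the participant agrees to the optional second PET/CT, taking 3 mSv per attenuation CT.

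If the confirmed dose is lower, the second figure should be reduced accordingly, for example to 11.18 mSv (22.4%) at 1.5 mSv.

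A further sentence should say that a repeat study requested by the treating physician would add up to another 9.68 mSv, or up to about 12.68 mSv if the optional scan is offered again. It should give no share of the annual limit, because the timing of the repeat is not fixed. The participant information should be checked for agreement.

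The cost is two sentences, one dose confirmation, an IRB modification and the check of the participant information. The stated exposure becomes less favourable for those who accept the second scan. No scan, activity or analysis changes.
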